2.1 Objectives & Hypotheses	<h3>2.1 Objectives and Aims</h3> 
Aims
 
1. To evaluate the determinants of Sustained Virologic Response (SVR) in patients treated with grazoprevir and elbasvir in the presence of immunosuppression (post-renal transplant). 
Primary Objective
 
1. To determine the difference in the host immune response as measured by interferon stimulated gene (ISG) expression (IP-10 in particular), and HCV specific T-cell response in post-renal transplant patients compared to historical, non-transplant patients and its association with SVR.2. To examine the efficacy of grazoprevir and elbasvir in patients post- renal transplantation compared to historical, non-transplant patients. 
Secondary Objectives
 
1. To evaluate the safety and adverse events of grazoprevir and elbasvir post-renal transplant patients compared to historical, non-transplant patients.2. To describe the effects of chronic HCV treatment on two-year renal allograft outcomes in patients treated after renal transplantation. <h4>2.1.1 Clinical hypotheses</h4> 
Primary Hypotheses
 
1. Patients treated for chronic HCV with grazoprevir and elbasvir after renal transplantation will maintain a robust host immune response as measured by ISG expression (IP-10 in particular) and HCV specific T cell responses in the presence of immunosuppression.2. The proportion of patients who achieve SVR12 will be greater than 90% in post-renal transplant patients. 
Secondary Hypotheses
 
1. The safety, tolerability, and adverse events of treatment with grazoprevir and elbasvir in patients with chronic kidney disease will not be significantly different in post-transplant patients compared to non-transplant patients.2. The treatment of chronic HCV using grazoprevir and elbasvir will improve the renal allograft outcomes in terms of rejection or graft survival. <h4>2.1.2 Clinical Impact</h4> 
Chronic HCV in patients with CKD is associated with an increased risk of death as well as renal transplant graft failures (1). With the FDA approval of grazoprevir and elbasvir, we now have a regimen that can be used in these patients with severe CKD. However, it remains unknown if there is an immunologic advantage for both achievement of SVR 12 and renal allograft outcomes in treating these patients prior to their transplant compared to waiting until after transplantation when they will be immunosuppressed. And while we predict that transplant recipients will maintain high rates of SVR, it is uncertain whether these immunosuppressed transplant recipients will maintain robust host immune responses to HCV treatment.

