Additionally, the effect of immunosuppression on the host response to HCV therapy is unknown. On the one hand, these patients could be treated for hepatitis C infection prior to renal transplantation to avoid the impact of immunosuppression as well as the impact of HCV-related liver and kidney disease on allograft function post transplantation. On the other hand, this approach will eliminate access to HCV positive kidneys (making the wait list time longer) and potentially reduce the efficacy of DAA therapy (due to drug-drug interaction between calcineurin inhibitors and HCV drugs). Recent studies have shown that grazoprevir is a weak inhibitor of CYP3A4 and may increase tacrolimus levels (approx. 40% above expected), though change has not been seen in elbasvir or grazoprevir levels (19) (8).

There are real benefits in waiting to treat HCV in patients until after transplantation in that it could decrease the wait time for transplantation by not necessitating a delay in transplant while completing HCV therapy and by permitting the use of HCV-positive kidney donors. Showing the impact that immunosuppression has on the host immune response to HCV during therapy would enable clinicians to decide whether patients should be treated before or after transplant, especially in cases where the wait for a transplant may be quite long.

2.3 Study Design	Experimental design The study will be a pilot, prospective, single-center, open-label, non-randomized, non-controlled clinical trial. 25 HCV genotype 1 infected post-renal transplant patients will be enrolled in the study. Recruitment will be conducted through the renal transplant and nephrology outpatient clinics at the University of Maryland.
-------------------------	--

Study population

The study will involve a single cohort of post-renal transplant patients.

All patients will have HCV genotype 1 chronic infections with active viremia and have no cirrhosis at the time of enrollment. All patients will additionally have stable renal function.

[figure not shown]
The post-transplant patients will include renal transplant recipients of both living donor and deceased donor organs infected with HCV prior to their transplantation with stable GFRs and active HCV viremia. These patients will also be recruited from the University of Maryland's multidisciplinary transplant nephrology clinic.

Inclusion criteria

- At least 18 years of age at the time of screening

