
2.7 Statistical Analysis and Sample Size Justification
	
Data analysis will be completed by the study biostatistician.
 
Primary Endpoints
 
Primary Objective 1. The primary endpoint for this objective will be the measurement of host immune responses using ISG expression including IP-10 levels, and HCV specific T-cell responses. ISG expression and IP-10 levels will be measured before and 4 weeks after completion of therapy. HCV specific T-cell responses will be measured before and during SVR 12 (12 weeks after completion of the study medications).
 
Primary Objective 2. The primary endpoint for this objective will be the measurement of SVR 12. This will be measured at study week 24/28, or 12 weeks after completion of the study medications.
 
Secondary Endpoints
 
Secondary Objective 1. We will assess the safety of the medications using adverse event monitoring. The primary endpoint for this objective will be the presence of any severe adverse event. A secondary endpoint will be the early discontinuation of the study medications. This will be assessed at the study visits weeks 0, 4, 8, and 12. Based upon prior trials with these investigational drugs, we estimate rate of serious adverse events of about 15% (17).
 
Secondary Objective 2. The primary endpoint for this objective will be episodes of rejection and graft survival for post-transplant patients after treatment and will be recorded via medical record abstraction as part of their enrollment in the ongoing prospective cohort study to assess treatment efficacy in chronic hepatitis C (HP – 00063362).
 
Research data will be collected and managed using REDCap (Research Electronic Data Capture) hosted at the University of Maryland, which is a secure, web-based application to support data capture for research studies. All of these variables will be entered into REDCap by study staff at the end of each study visit based upon the labs obtained, patient questionnaires, and interim records reviews, and after the initial 30 to 34 weeks of the study based upon medical records reviews.
 
Statistical Methods
 
Clinical treatment arm
 
All statistical analyses will be based on an intention-to-treat model, including all enrolled patients who received at least one dose of study medication. Both the primary efficacy and safety endpoints will be based on the proportion of patients with SVR 12 and severe adverse events, respectively, with point estimates and 95% confidence interval. Both primary efficacy and safety endpoints will be compared to a non-transplant, HCV-infected historical control group by using two-sided, exact one-sample binomial test at a significance level of 0.05. Demographic and baseline characteristics will be summarized using standard descriptive statistics overall and by patient cohort. Univariate logistic regression will be performed to identify baseline factors associated with SVR 12 at a significance level of 0.05.
 
Measurement of host immune response

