
	
Mann-Whitney or Wilcoxon matched-pairs signed rank test will be used for 2-group comparisons, and a linear mixed-effects model will be used for multigroup longitudinal comparisons with fixed effects for group (SVR versus relapse), time, and group/time interaction. A significant group/time interaction would indicate that the 2 groups had different patterns over time. A class variable will be used for time to allow an arbitrary average time pattern within a group. In addition to fixed effects summarizing average group responses over time, the model will accommodate random, patient-specific deviations in intercept and time effects. Correlations will be assessed by nonparametric Spearman rank correlation. Spotfire S+ 8.2 (TIBCO), Prism 6.0 software (GraphPad), and SAS 9.3 (SAS Institute, Inc.) will be used for statistical analysis and data presentation using a p-value of 0.05 to indicate statistical significance.
 
Power/Sample Size:
 
This is a pilot, prospective clinical trial comparing the host immune response using ISG expression, including IP-10 levels, and HCV specific T-cell responses between a historical, non-transplant cohort of 25 patients from IRB approved studies previously conducted at the IHV and post-renal transplant (immunosuppressed) patients and its association with SVR 12. The study team will perform an interim data and safety evaluation for the efficacy, safety, and tolerability of grazoprevir and elbasvir therapy. Data analysis will focus on the clinical efficacy endpoint of SVR 12 with secondary analysis looking at the relationship of the host immune response markers with the primary endpoint of SVR 12 in both groups.
 
We anticipate enrollment of 25 patients in this arm of the study. This will be compared to a historical control group of 25 patients with stored blood samples from previous IRB approved clinical trials conducted at the IHV.
 
We anticipate a SVR 12 of greater than 90% in the grazoprevir plus elbasvir treatment group post-renal transplantation. With 50 participants (25 in this study and 25 historical controls), the study will be able to estimate the difference in SVR12 proportions to within ± 0.18 (Table 2). Table 2 shows a substantial gain in precision by increasing the sample size from 15 per arm to 25 per arm; however, the effect diminishes beyond 25.
 
Table 2: Sample Size Calculation for SVR12
 
  
 N per arm	15	20	25	30	50	
   
 Accuracy to within \pm	0.24	0.20	0.18	0.17	0.13	
  
	N per arm	15	20	25	30	50	Accuracy to within \pm	0.24	0.20	0.18	0.17	0.13

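### Primary Hypothesis 1 predicts a maintained immune response, but the plan compares the cohorts only with a difference test and gives no interval showing how large a loss is excluded

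*Combined protocol and SAP*

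**What the plan says.** Primary Hypothesis 1 in Section 2.1.1 predicts that transplant recipients "will maintain a robust host immune response as measured by ISG expression (IP-10 in particular) and HCV specific T cell responses" while immunosuppressed. Neither the size of a robust response nor what would count as maintaining it is defined.

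Primary Objective 1 in Section 2.1 is worded differently: "To determine the difference in the host immune response as measured by interferon stimulated gene (ISG) expression", together with HCV-specific T-cell response, in transplant patients against historical non-transplant patients. Section 2.5.2 describes comparing the change in ISG expression and IP-10 between two groups, from before therapy to 4 weeks after its completion. T-cell responses are measured before therapy and at SVR12.

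The immune-response methods in Section 2.7 have three elements:
- "Mann-Whitney or Wilcoxon matched-pairs signed rank test will be used for 2-group comparisons";
- a mixed model with "fixed effects for group (SVR versus relapse), time, and group/time interaction";
- Spearman correlations.

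The only criterion is "using a p-value of 0.05 to indicate statistical significance". Sidedness is not given for these markers. The "two-sided, exact one-sample binomial test at a significance level of 0.05" applies to SVR12 and severe adverse events, which are also the only endpoints with a planned 95% confidence interval.

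On size, Section 2.7 says "We anticipate enrollment of 25 patients in this arm of the study", to be compared with 25 historical patients who have stored samples. Table 2 gives precision for the difference in SVR12 only.

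**The concern.** The hypothesis is favourable when there is no important loss. The mixed model cannot test this against the historical cohort, because its group factor is virologic outcome, not transplant status. Of the listed methods, only the Mann-Whitney test suits two unpaired cohorts, and it can only show that they differ. If it does not reject, the plan supplies nothing to say how large a loss remains possible.

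This matters because Section 2.2 expects that showing the impact of immunosuppression on the host response "would enable clinicians to decide whether patients should be treated before or after transplant". If the comparison is non-significant and no interval is reported, a reader is left to decide what it means. Fewer usable stored samples would also make non-significance more likely, so weaker data would look more favourable. The same habit of thought appears in Secondary Hypothesis 1, which frames comparable safety as the absence of a significant difference.

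**Working it through.** **Inputs from the documents.** 25 patients per cohort and significance at 0.05 (Section 2.7); outcome is pre-to-post change per patient (Section 2.5.2).

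**Assumptions, because the documents give no figure.** Two-sided test; complete pairs in all 50 patients; normally distributed change on the log scale; losses of 0.3 to 1.0 SD as the range of interest.

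**1. The plan's own precision figure.** Half-width for a difference in proportions = 1.96 × √{[p1(1−p1) + p2(1−p2)]/n}. The historical SVR12 rate is not stated. With an assumed 0.90 and 0.85, n = 25 gives 1.96 × √[(0.0900 + 0.1275)/25] = 0.183. For n = 15, 20, 30 and 50 the formula gives 0.236, 0.204, 0.167 and 0.129. All five entries of Table 2 are matched. (0.90 in both arms gives 0.166 at n = 25 and does not match.) So Table 2 reproduces under that assumption, but it says nothing about the immune markers.

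**2. Power of the difference test.** For a true loss of d SD, the normal approximation is Φ(d√(n/2) − 1.96). At d = 0.5: 0.5 × √12.5 = 1.768, and Φ(1.768 − 1.960) = 0.424. The noncentral t gives 0.410. Simulating the Mann-Whitney test on normal data gives about 0.38.

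| True loss (SD) | Normal | t-test | Mann-Whitney (simulated) | Missed by Mann-Whitney |
|---|---|---|---|---|
| 0.3 | 18% | 18% | 17% | 83% |
| 0.5 | 42% | 41% | 38% | 62% |
| 0.8 | 81% | 79% | 76% | 24% |
| 1.0 | 94% | 93% | 92% | 8% |

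If the test were one-sided at 0.05, a half-SD loss would still be missed about 45% to 46% of the time (normal and t).

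**3. Width of the interval the plan omits.** t(0.975, 48) × √(2/25) = 2.011 × 0.283 = 0.57 SD. A rank-based interval is slightly wider on normal data: with efficiency 0.955, 0.569/√0.955 = 0.58 SD. An observed difference of zero therefore gives roughly −0.57 to +0.57 SD, which includes a half-SD loss. An observed loss just short of significance (about 0.57 SD) gives an interval reaching 0.57 + 0.57 = 1.14 SD.

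**4. Missing samples.** With 20 evaluable per group, t-test power at 0.5 SD falls from 41% to 34%. The half-width grows to 2.024 × √(2/20) = 0.64 SD.

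**5. What a margin would demand.** With no true loss, the chance that the limit on the side of loss falls inside a margin of m SD is essentially the power at a shift of m. For a rank-based interval this is about 38%, 76% and 92% for margins of 0.5, 0.8 and 1.0 SD. A 0.5-SD margin at 80% power needs 2 × (1.960 + 0.842)²/0.5² = 62.8, so 63 per group (normal approximation).

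**The case against.** Four points on the other side deserve weight.

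- **A difference test fits the objective.** Primary Objective 1 asks for a difference, and the hypothesis itself names no comparator. This stands, and it probably explains the choice of test. It leaves the hypothesis without a matching analysis in the comparison the objective sets up.
- **The study is a pilot.** Section 2.7 says that analysis will focus on SVR12, with the markers' relation to SVR12 as a secondary analysis. That is a fair reason not to demand a formal non-inferiority design. It is not a reason to omit an interval, since a pilot is chiefly for estimation. The immune response is also still listed as the first primary objective.
- **A within-cohort result could count.** A reader might infer that failure to reject is the only result that could support Hypothesis 1. The documents do not support that. If a robust response just means a clear change in transplant patients, a significant signed-rank test would support it. That is a weaker claim: it does not show the change to be as large as in non-transplant patients.
- **No rule equates non-significance with maintenance.** A reader might infer that the team intends to declare the response maintained when p exceeds 0.05. No section says so. The sentence in Section 2.2 about guiding clinicians concerns showing an impact, not a null result. The risk is a gap in the plan, not a stated error.

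The half-SD loss and the two-sided level are also assumptions. The miss rate runs from 83% to 24% between 0.3 and 0.8 SD, so the 62% figure should not be quoted without its effect size.

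**Conclusion.** The concern holds in a limited form. For the comparison with historical patients, the plan offers a difference test and no interval, so a non-significant result could not support Primary Hypothesis 1. Under the stated assumptions, Mann-Whitney power is about 17%, 38% and 76% for losses of 0.3, 0.5 and 0.8 SD, and the 95% half-width is about 0.57 SD. The link between the Mann-Whitney test and the cohort comparison is inferred from Sections 2.5.2 and 2.7; the plan does not state it.

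It would go too far to say that the trial must become a non-inferiority study or is too small for its purpose. The documents give no SD and no relevant difference for any marker, so no margin can be derived from them. A wide margin without a clinical basis could itself certify a sizeable loss as maintenance. The change is worth making because it is nearly free and alters what the trial can conclude.

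**What to change.** **In Section 2.7, immune-response methods:**
- For each primary immune marker, report the transplant-minus-historical shift in pre-to-post change as a Hodges-Lehmann estimate with 95% CI. Use log2 fold change for ISG and IP-10, and change in spot count for ELISPOT.
- State for each marker which direction is a weaker response. Section 2.5.2 describes ISG and IP-10 as falling on therapy and T-cell responses as rising.
- State which sample is A and which is B in the ISG fold change. Section 2.5.2 takes ΔCt as GAPDH minus target and then raises 2 to −ΔΔCt, so the result expresses B relative to A.
- Base the conclusion on Hypothesis 1 on these intervals, and state that non-significance will not be read as maintenance.

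**In Power/Sample Size:** add that 25 versus 25 complete pairs gives an interval of about ±0.57 SD, which cannot exclude a half-SD loss even if the observed difference is zero.

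**Optional:** a formal margin for declaring the response maintained, only if the sponsor can justify one before the transplant samples are assayed. The quoted power should then match the rank-based interval (about 38%, 76% and 92% for margins of 0.5, 0.8 and 1.0 SD with no true loss). The plan should also say whether every primary marker must meet its margin.

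**Cost:** wording and one interval per marker from data already planned, with no added patients, samples or visits. The downside is that the trial can claim maintenance less often.

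### As worded, the safety hypothesis is met by a failure to reject, and at n = 25 a doubled event rate would go undetected about half the time or more

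*Combined protocol and SAP*

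**What the plan says.** Section 2.1.1, Secondary Hypotheses, item 1, predicts that safety, tolerability and adverse events "will not be significantly different in post-transplant patients compared to non-transplant patients".

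Section 2.7 supplies the rest:

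- Endpoint (Secondary Endpoints, Secondary Objective 1): "The primary endpoint for this objective will be the presence of any severe adverse event".
- Expected rate (same paragraph): "we estimate rate of serious adverse events of about 15" per cent, citing the earlier trial in chronic kidney disease.
- Comparison (Statistical Methods, Clinical treatment arm): "Both primary efficacy and safety endpoints will be compared to a non-transplant, HCV-infected historical control group", by a "two-sided, exact one-sample binomial test at a significance level of 0.05". The same paragraph commits to a point estimate and 95% confidence interval for the safety proportion.
- Size (Power/Sample Size): "We anticipate enrollment of 25 patients in this arm of the study", set against a "historical control group of 25 patients with stored blood samples".

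The plan gives no null proportion, equivalence or non-inferiority margin, acceptable upper limit, or power for safety. Table 2 is headed as a calculation for SVR12 only.

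**The concern.** The hypothesis is phrased as the absence of a significant difference, and the one test attached to it is built to detect a difference. Followed literally, the data support the hypothesis whenever the test fails to reject, and a small sample makes that more likely whatever the true event rate is. The fewer the patients, the easier the hypothesis is to meet.

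What is at stake is the safety statement in the final report. Section 2.2 presents the study as informing whether to treat HCV before or after transplant, in a population on immunosuppression where it says little is known. A statement that safety did not differ significantly could be carried into that question although the data were compatible with a much higher event rate.

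**Working it through.** **The plan's own figure.** The only sample-size figure is ±0.18 for the SVR12 difference at 25 per arm. It reproduces as a Wald half-width if the control rate is taken as 85%, which the plan does not state: 1.96 × √[(0.90×0.10 + 0.85×0.15)/25] = 1.96 × √0.0087 = 0.183. With both rates at 90% it is 0.166. Either way it says nothing about safety, so the safety test has to be evaluated from first principles.

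**Inputs.** n = 25 and two-sided α = 0.05 (Section 2.7). Null p0 = 0.15 is an assumption: it is the only safety rate in the plan, but it is not named as the null. The true rate of 0.30 is a scenario chosen here. X is the number of patients with an event, X ~ Binomial(25, p).

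**Step 1: where the test rejects, p0 = 0.15.** Section 2.7 does not say which two-sided exact version applies, so both are shown. The first sums the probabilities of all outcomes no more likely than the one observed. The second doubles the smaller tail.

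| Events | Relevant tail | p, small-probability version | p, equal-tail version |
|---|---|---|---|
| 0 | P(X=0) = 0.0172 | 0.0172 + P(X≥9) 0.0080 = 0.025 | 0.034 |
| 7 | P(X≥7) = 0.0695 | 0.0695 + 0.0172 = 0.087 | 0.139 |
| 8 | P(X≥8) = 0.0255 | 0.0255 + 0.0172 = 0.043 | 0.051 |
| 9 | P(X≥9) = 0.0080 | 0.008 | 0.016 |

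The first version rejects at 0 or at 8 and above (actual size 0.0255 + 0.0172 = 0.043). The second rejects at 0 or at 9 and above. So 1 to 7 patients with an event (4% to 28%), or 1 to 8 (4% to 32%), are not significantly different from 15%.

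**Step 2: chance of missing a doubling to 30%.**

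- Small-probability version: P(1≤X≤7 | 0.30) = 0.5118 − 0.0001 = 0.512, so power is 0.488.
- Equal-tail version: P(1≤X≤8 | 0.30) = 0.6769 − 0.0001 = 0.677, so power is 0.323.

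For the first version, power at true rates of 20%, 25% and 35% is 0.113, 0.274 and 0.694.

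**Step 3: other null values.** Chance of missing a doubling:

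| p0 to 2×p0 | Small-probability | Equal-tail |
|---|---|---|
| 10% to 20% | 62% | 78% |
| 15% to 30% | 51% | 68% |
| 20% to 40% | 42% | 42% |

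Because the counts are discrete, the figure moves unevenly between these values. In steps of one percentage point the lowest is 35%, at p0 = 19% in the first version (rejects at 0 or at 9 and above; P(1≤X≤8 | 0.38) = 0.346).

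**Step 4: sampling error in the controls.** The one-sample test treats the control rate as known. If it were estimated from the 25 historical patients and compared by Fisher's exact test, 30% against 15% would be missed 85% of the time.

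**Step 5: what the interval would show.** At 7/25 (28%) the exact 95% CI is 12.1% to 49.4%. The result is non-significant, yet the interval reaches more than three times 15% (0.494/0.15 = 3.3).

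**The case against.** The strongest reply is that the plan never states the inference at issue. Section 2.1.1 lists predicted results, the matching objective in Section 2.1 is only to evaluate safety, and no sentence says that a p-value above 0.05 will be taken as proof of equal safety. A reader might infer that the trial has committed itself to certifying similar safety; the documents do not support that. What stands is narrower: the hypothesis is defined by non-significance, one test is attached to it, and nothing in Section 2.7 rules out that reading.

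Second, a 95% CI for the safety proportion is already planned, so a report of 7/25 would display the wide interval next to the p-value. This is a real mitigation. It does not settle the matter, because no conclusion is tied to the interval.

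Third, the figures rest on choices the plan leaves open. The 15% is an expected rate for serious events, while the tested endpoint is severe events; Sections 2.9.2 and 2.9.3.1 define these separately, so the rate may not belong to the endpoint. The null and the version of the exact test are also unspecified. This is fair, and it is why ranges are given. Of these choices, the equal-tail version and the two-sample comparison make a miss more likely at 15%, while some higher null values make it less likely.

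Fourth, this is a secondary endpoint in a pilot, and the DSMB in Section 2.9.6 reviews adverse events every six months and can halt the study. Participant protection therefore does not hang on this test. That bears on severity, and does not make the hypothesis test informative.

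**Conclusion.** The point holds in a limited form. The safety hypothesis as worded is satisfied by a failure to reject, with no margin, and the test attached to it has little power at n = 25. With an assumed null of 15%, a doubling to 30% is missed 51% of the time, or 68% with the equal-tail version; at nulls of 10%, 15% and 20% the range is 42% to 78%. These figures rest on 25 analysed patients, on 15% serving as the null, on that rate applying to the endpoint actually tested, and on doubling as the scenario. The logical flaw needs none of those assumptions.

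It should not be put as a claim that the plan declares equal safety on a non-significant result, or that it omits estimation; neither is so. The change is worth making because it is almost free and the planned interval already provides most of what is needed.

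**What to change.** - **Section 2.1.1:** restate the secondary safety hypothesis as estimation of the event proportion in post-transplant patients.
- **Section 2.7, conclusion:** base the safety conclusion on the 95% CI already planned, specify that it is exact, and show it beside the historical control proportion with its own 95% CI. State that a non-significant p-value will not be taken as evidence of similar safety.
- **Section 2.7, definitions:** say whether the endpoint is severe or serious events and make the expected rate match. If the test is kept, name its null value and the version of the exact test.
- **Optional:** if the sponsor wants to claim similarity, fix an upper limit in advance, claim similarity only if the upper confidence limit lies below it, and otherwise report the comparison as inconclusive.

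The cost is wording, with no added patients or data, and a weaker claim about safety. The optional rule would often end as inconclusive. For illustration only, with an assumed limit of 30%, the exact 95% upper limit is 26.0% at 2/25 and 31.2% at 3/25, so at most 2 patients could have an event. The chance of that is P(X≤2 | 0.15) = 25% when the true rate is 15%. The choice of limit belongs to the sponsor.
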